6.4 Discussion of trial design

We recently conducted a clinical trial showing that oral co-administration with Bif195 can reduce the risk of low-dose ASA-induced intestinal ulceration in humans using serial VCE as our main efficacy parameter¹¹ (ClinicalTrials.gov ID number: NCT03228589).

For the present trial, we will re-use this clinical challenge model that we have already established and tested. A mild deterioration of the upper small-intestinal mucosa will be induced by ASA, a chemical agent commonly used and with well-established injurious effects on the small intestine. Based on the dataset from our previous trial, we observed that 300 mg of ASA daily for 4-6 weeks represents a relevant challenge model, both in terms of daily dose and duration, and ability to induce a mild deterioration in the small intestine as observed with VCE.

A run-in period is included to wash out the potential impact of any pre-study probiotic products. The 6 weeks between visit 3 and 4 serve the purpose as wash-out for any Bif195 effects as well as recovery of the mucosal tissue between the ASA challenge periods. A cross-over design was chosen to obtain the statistical benefits of the subjects being their own controls.

6.4.1 Inclusion Criteria

For a subject to be eligible for the trial, all the below criteria must be checked with a “yes”:

- Written informed consent
- Healthy and without any gastrointestinal discomfort/pain/symptoms
- Age ≥ 18 and ≤ 40 years at the day of screening
- Willing and able to abstain from any other probiotic products and/or medication known to alter gastrointestinal function throughout the participation of the trial

6.4.2 Exclusion Criteria

For a subject to be eligible for the trial, all the below criteria must be checked with a “no”:

- Abdominal surgery which, as judged by the Investigator, might affect the GI function (except appendectomy and cholecystectomy)
- History of peptic ulcer disease
- Known history of *Helicobacter Pylori* infection
- Any known bleeding disorder
- Allergy to ASA
- Resting diastolic blood pressure ≥ 95 mmHg
- Resting systolic blood pressure ≥ 150 mmHg
- A current diagnosis of psychiatric disease

- Systemic use of antibiotics, steroids (except contraceptives) or antimicrobial medication in the last month
- Daily usage of non-steroidal anti-inflammatory drugs in the last 2 months or incidental use in the last 2 weeks prior to screening (ASA, Ibuprofen, Diclofenac, Naproxen, Celecoxib, Mefenamic acid, Etoricoxib, Indometacin)
- Usage of medications, except contraceptives, in the last 2 weeks prior to screening
- Regular use of probiotics in the last month
- Use of laxatives, anti-diarrheals, anti-cholinergics and proton pump inhibitors within last 2 months prior to screening
- Use of immunosuppressant drugs within last 4 weeks prior to screening
- Diagnosed inflammatory gastrointestinal disease and/or irritable bowel syndrome
- Any other disease that, by the Investigators discretion, could interfere with the intestinal barrier function of the subject
- Participation in other clinical trials in the past 2 months prior to screening
- Smoking and/or frequent use of other nicotine products
- Higher alcohol intake than what the board of Health recommends
- Desire and/or plans to change current diet and/or exercise regime during the participation of this trial
- For Women: Pregnancy or lactation

6.4.3 Subject Withdrawal Criteria

Participation in the trial is voluntary, and subjects have the right to withdraw from the trial at any time without providing a reason, and with no loss of benefits to which the subject is otherwise entitled. If a trial subject chooses to withdraw, the trial personnel must be informed immediately, and every effort should be made to complete the end-of-trial assessments and document the reason for discontinuation in the case report form (CRF). The Sponsor should be notified as soon as possible about any discontinued subjects.

Any subject who prematurely terminates participation and who has consumed the test or reference product at least once will be asked to undergo a final examination (end-of-trial visit/early termination visit). For subjects considered lost to follow-up, the CRF will be completed up to the last visit.

The Investigator has the right to terminate participation of any subject at any time if they deem it in the subject's best interest.

Examples of possible reasons for premature withdrawal of a trial subject include, but are not limited to:

- Subject withdraws consent for personal reasons
- Subject's general condition and/or data from the visit 2 gastroscopy procedure contraindicates continuing the trial, as judged by the trial personnel and/or the principal Investigator

- Participation in other clinical trials during participation of this trial
- Significant non-compliance with trial protocol or general lack of cooperation
- Pregnancy
- A serious adverse event (SAE)
- Lost to follow-up
- Any other reason as determined by the principal Investigator

6.5 Investigational Products

6.5.1 Identification and Description of Investigational Product

Bifidobacterium is a genus of lactic acid- and acetic acid-producing, gram-positive, non-spore forming, non-motile, anaerobic bacteria. They are common constituents of the microbiota in the human intestinal tract.

The investigational product is a vegetable capsule containing *Bifidobacterium breve* DSM 32356, name simplified to Bif195 throughout this document.

The reference product (placebo) is the same capsule, but without Bif195. All products will be produced at Chr. Hansen laboratory in Hørsholm, Denmark, which is certified for food production.

The CFU stability of the production batch of *Bifidobacterium breve* DSM 32356 that will be used in this trial will be monitored closely during the trial. The internal analyses at Chr. Hansen A/S indicate that the specific product stability loss is approximately 25% during the product shelf life, and we expect that the CFU per capsule will be minimum $50*10^9$ CFU per capsule at the time of trial intervention. The CFU stability of the investigational product batch will be analysed in parallel with performing this trial and these data will be available and included in the final clinical trial report.

Table 2 Composition of investigational product

	Placebo capsules	Probiotic capsules Bifidobacterium breve
Manufacturing	Chr. Hansen A/S, Denmark	Chr. Hansen A/S, Denmark
Brief description	Capsules with excipients only	Capsules containing Bifidobacterium breve DSM 32356 and excipients
Capsules	Size 1 HPMC capsules	Size 1 HPMC capsules
Capsules shell	73.6 mg Hypmellose 1.4 mg Titanium dioxide	73.6 mg Hypmellose 1.4 mg Titanium dioxide
Active Ingredients	None	Bifidobacterium breve DSM 32356
Excipients	Microcrystalline Cellulose 6 mg per capsule Magnesium Stearate 1.5 mg per capsule Maltodextrin 277.8 mg per capsule Sodium Ascorbate 14.7 mg per capsule	
Supplied as	CSP Activ-Vials containing 24 capsules in each vial	
Storage conditions	Store at +2-8 °C	

6.5.2 Labelling

The trial products will be labelled according to the standard procedures of the clinical site in a manner so that every person with an active role in the conduct of the trial will remain blinded. The labels on the trial products will as minimum bear the following information:

Master label text
Trial code: HND-GI-036
Sponsor: Chr. Hansen A/S
Principal Investigator: [name]
Capsule with or without probiotic
1 capsule with breakfast
1 capsule in the evening
Randomisation number: XXXX
Expiry date: April, 2021
To be stored at +2-8 °C
For clinical trial use only

6.5.3 ASA challenge product

The ASA product used during the ASA challenge periods will be the 300 mg Aspirin from Alliance Pharmaceuticals Ireland.

6.5.4 Blinding

Both active (Bif195) and reference (placebo) product will be similar in smell, taste and appearance. All trial products will be packaged in identical packs with identical labelling, except for the randomisation number.

Trial subjects, the clinical team and the sponsor will all be blinded during the entire trial until database lock is performed. Only one or two appointed Trial Supply Coordinators, not otherwise involved in the conduct of the trial, will be un-blinded as necessary to perform labelling of the product.

An emergency unblinding procedure will be established to allow the principal Investigator the option of disclosing the product assignment for an individual subject if clinical circumstances require such an unblinding. Unblinding will only be performed if medical decisions should be taken which mandate knowledge about the treatment received. The Sponsor will be informed immediately and before unblinding in case a subject will be unblinded by the Investigator. In the event, that emergency disclosure of product assignment is required, the subject will be withdrawn from further participation in the trial.

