4.5 Protocol Deviations

No systematic deviations from the protocol are allowed, and no protocol waivers will be given. All protocol deviations noted during the trial will be recorded and evaluated as major or minor by the Sponsor before the blinding is broken.

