6.5.5 Method of Assigning Subjects to Treatment Groups

Prior to the start of the trial, the allocation of subject numbers to trial groups will be performed by randomisation lists organised by an un-blinded partner not otherwise involved in the trial conduct.

Particularities of the randomisation – such as variable or fixed block length, or no block length at all – will be stated in the randomisation list itself. Neither the investigator site nor the sponsor will receive any information about randomisation blocks.

At screening, subjects will be assigned a screening number starting at 1, according to their chronological entry into the trial. As an example, the first subject will have screening number 1.

If the subjects are suitable for trial participation, they will receive their 4-digit randomisation number at Visit 2, starting with number 1001.

Access to the randomisation list is limited to the unblinded partner that will generate the list and to the appointed Trial Supply Coordinators, not otherwise involved in the conduct of the trial, who will label the products according to the randomisation list.

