6.9.8 Statistics and power calculation

Data will be entered into a database and analysed using statistical software. The effect of the intervention on the endpoints will be assessed using paired statistical analysis and the level of significance will be set to 0.05. Pathway analysis will also be performed using a more explorative approach.

Previous studies using the same endoscopy procedure with biopsies being analysed for arrays of gene expression have showed an approximate negative binomial distribution and a coefficient of variation of 0.344. Assuming a negative binomial distribution of the data in the present study, we have calculated that a sample size of 20 will result in a power of 0.95 for identifying genes that are down or up-regulated more than 1.5-fold as a consequence of Bif195 intervention at a significance level of 0.05. In order to achieve this statistical power, we aim to have 20 subjects completing the intervention. Assuming a drop-out rate of around 20%, we aim to randomise 25 subjects.

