6.10.6 Reporting of Serious Adverse Events

If an SAE occurs, trial personnel must fill in a “Serious Adverse Event reporting form” and notify the Investigator immediately. The Investigator should report all SAEs (whether or not considered related to trial treatment) to the Sponsor within 24 h after awareness of the SAE. The reporting by the Investigator to the Sponsor should cover the seriousness criteria, intensity and initial causality assessment.

The initial report of a SAE should as far as possible be supplemented by detailed information on diagnosis/symptoms, the relationship with the start of treatment and the latest dose of trial treatment taken and any further relevant data. A follow-up report of the SAE will be written as applicable and sent to the Sponsor.

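### Section 6.5.4 requires sponsor notice before any emergency code break, with no exception for urgent cases; prior notice should apply only when time allows

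*Protocol*

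**What the plan says.** Protocol section 6.5.4 (Blinding) sets the emergency rule in four steps.

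- A procedure is promised: "An emergency unblinding procedure will be established to allow the principal Investigator the option of disclosing the product assignment for an individual subject".
- Its use is restricted: "Unblinding will only be performed if medical decisions should be taken which mandate knowledge about the treatment received".
- The order of events is fixed: "The Sponsor will be informed immediately and before unblinding in case a subject will be unblinded by the Investigator".
- The consequence for the subject is stated: "the subject will be withdrawn from further participation in the trial".

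Two other sections bear on how this works in practice. Section 4.5 says: "No systematic deviations from the protocol are allowed, and no protocol waivers will be given". It adds that the sponsor grades recorded deviations as major or minor. Section 6.5.5 says who holds the code: "Access to the randomisation list is limited to the unblinded partner that will generate the list and to the appointed Trial Supply Coordinators". The protocol describes no code held at the site and no out-of-hours route to it in the text available for this review.

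The SAP contains no unblinding procedure.

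**The concern.** The restriction and the ordering in 6.5.4 pull against each other. The only cases allowed to reach a code break are those in which treatment depends on the assignment, and these are the cases where a prior administrative step is hardest to justify. As written, the investigator in an urgent case has two options: notify the sponsor first, or act first and deviate from the protocol.

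What is at stake is subject safety and clarity for the investigator. Sample size, error rates and the analysis of every endpoint are untouched.

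**Working it through.** No arithmetic bears on the defect itself, so the check is of the text. The only calculation concerns the cost of the remedy.

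**1. Is the prior-notice rule conditional?** The notice sentence in 6.5.4 carries no qualifier such as *if possible* or *when time allows*. The sentence before it limits unblinding to decisions that need the assignment, but does not separate urgent from non-urgent decisions. The rule therefore covers every code break by the investigator.

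**2. Does another section supply an exception?**

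| Section | Subject | Timing of notice for a code break? |
|---|---|---|
| 4.4 Protocol Changes | Protective measures against immediate hazards, and informing the ethics committee of new events | No |
| 4.5 Protocol Deviations | No waivers; deviations recorded and graded | No exception |
| 6.5.5 Method of Assigning Subjects | Who may see the randomisation list | No |
| 6.6.2 Assessment of Safety | Subjects may call a trial doctor at any time | No |
| 6.10 to 6.10.7 | Adverse event handling; SAE reports go "to the Sponsor within 24 h after awareness of the SAE" | No; the 24 h window is for SAE reports |
| 6.10.8 Procedures in Case of Medical Emergency | Listed in the table of contents; body text not available for this review | Unknown |
| SAP | No unblinding procedure | No |

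No exception appears in the available text. One in 6.10.8 cannot be ruled out.

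**3. What follows from sections 6.5.4 and 4.5 together?** Because 6.5.4 puts notice first and 4.5 grants no waivers, breaking the code and notifying afterwards is a deviation. A single event is not a systematic deviation, so the consequence is an entry to be graded. Section 4.5 does not forbid urgent care.

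**4. Is an urgent case conceivable?** Section 5.2 names bleeding, infection and perforation as rare complications of gastroscopy, and each subject has four gastroscopies with biopsies (Visits 2 to 5). It is an inference, not something the protocol states, that a physician treating a severe infection might want to know at once whether the subject had been taking live bacteria.

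**5. How much delay does the rule add?** The documents give neither a frequency of code breaks nor a notification time, so no figure can be derived. Under 6.5.5 the investigator may need to contact someone outside the site to obtain the code in any event. The extra time due to sponsor notice is therefore not established.

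**6. What would one unnecessary code break cost?** Section 6.9.8 gives the inputs: "we aim to have 20 subjects completing the intervention. Assuming a drop-out rate of around 20%, we aim to randomise 25 subjects".

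- Planned losses: 25 − 20 = 5, and 5/25 = 20%, which matches the stated drop-out rate.
- One withdrawal as a share of those randomised: 1/25 = 4%.
- One withdrawal as a share of the planned losses: 1/5 = 20%.

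The synopsis allows withdrawn subjects to be replaced, so even this loss can be made good.

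**The case against.** The strongest opposing case is that this is a wording preference with no demonstrated harm.

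- **Notice is not approval.** 6.5.4 requires no reply and no waiting period, and a message sent as the code is requested would comply. This stands and limits the harm, but notice remains a precondition.
- **The governing detail lies elsewhere.** 6.10.8 was not available and the emergency procedure is still to be established; either may settle the matter. This stands as a limit on what can be said about the protocol as a whole. It does not rescue the sentence in 6.5.4: an exception elsewhere would contradict it, and a procedure written to match 6.5.4 would carry the same rule forward.
- **The scenario is remote.** Only a probiotic versus excipients is masked, and aspirin, the agent known to injure the mucosa, is given to everyone in both periods. Sections 5.2 and 6.6.2 report no adverse events attributed to Bif195 in earlier trials, and section 5.3 reports susceptibility to all eight antibiotics tested. No decision that would turn on the assignment within minutes has been identified. This stands, and is the main reason the point ranks low.
- **The real bottleneck is access to the code.** Rewording the notice rule achieves little if the investigator still cannot reach the list. This also stands, and the remedy has to cover it.

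**Conclusion.** The point holds as a minor improvement. Section 6.5.4 makes sponsor notice a precondition of every emergency code break, and no available section relaxes this for urgent cases. An investigator who put immediate care first would deviate from the protocol.

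The practical risk is small and unquantified, and no estimate, sample size or analysis changes. Confidence is medium, because the conclusion concerns what 6.5.4 states. Whether the protocol as a whole lacks an exception depends on 6.10.8 and on the procedure still to be written.

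**What to change.** Reword the notice sentence in 6.5.4 along these lines:

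- The investigator may break the code at once when urgent care requires it.
- The sponsor is told beforehand only when time allows.
- Otherwise the sponsor is told promptly afterwards that a code break occurred, for example within the 24 h already used for SAE reports. The assignment is not disclosed, so sponsor blinding is kept.

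Check 6.10.8 against this and align it where needed. Write the emergency unblinding procedure to match, with a direct route by which the investigator can obtain a single subject's code despite the restricted list access in 6.5.5. The decision whether to unblind and how to treat stays with the physician.

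The cost is one sentence in 6.5.4 plus consistency in 6.10.8 and the procedure. The downside is that, in urgent cases, the sponsor can no longer question a code break before it happens. The price of an unnecessary one is a single, replaceable subject.

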6.5.5 Method of Assigning Subjects to Treatment Groups

Prior to the start of the trial, the allocation of subject numbers to trial groups will be performed by randomisation lists organised by an un-blinded partner not otherwise involved in the trial conduct.

Particularities of the randomisation – such as variable or fixed block length, or no block length at all – will be stated in the randomisation list itself. Neither the investigator site nor the sponsor will receive any information about randomisation blocks.

At screening, subjects will be assigned a screening number starting at 1, according to their chronological entry into the trial. As an example, the first subject will have screening number 1.

If the subjects are suitable for trial participation, they will receive their 4-digit randomisation number at Visit 2, starting with number 1001.

Access to the randomisation list is limited to the unblinded partner that will generate the list and to the appointed Trial Supply Coordinators, not otherwise involved in the conduct of the trial, who will label the products according to the randomisation list.

6.5.6 Selection of Dosages

The active test product will contain approximately $100*10^9$ CFU of Bif195 per day in the active treatment part of the trial. In a previous trial run by Chr Hansen A/S with a 6-week ASA challenge regime, a daily dose of $50*10^9$ CFU of Bif195 per day was used.

6.5.7 Administration of Trial Treatment for Each Subject

The subjects will consume one tablet of 300 mg ASA daily for 4 weeks, 28 days, in each trial period together with breakfast. If a subject forgets to consume a dose of ASA, it can be taken later on the same day, with or without a meal, but an additional dose should not be taken on the following day to compensate for a missing dose on the day before.

The subjects will consume 2 capsules of trial product (Bif195/active or placebo) daily during the 4 weeks, 28 days, treatment period. One of the capsules should be taken with the subject's breakfast, but preferably 10 minutes before intake of the ASA. The other capsule should be taken in the evening, with or without a meal.

In order to allow 3 days of healing of the mucosal wall after biopsies, the first administration of ASA and trial product will take place at breakfast on the 4th day after Visit 2 and again on the 4th day after visit 4.

6.5.8 Compliance

Subjects will return all unused ASA and trial product at Visits 3 and 5 for accountability as dictated in the flow chart. Subjects consuming $\geq 80\%$ of expected ASA tablets between Visit

2 and Visit 5 and $\geq 80\%$ of trial product between Visit 2 and Visit 5 will be considered compliant with this protocol.

6.5.9 Accountability and Disposal

The site will keep proper accountability records at a subject level and at a site level. Subjects must return unused vials and capsules/tablets to the site for accountability. The trial personnel will keep accurate records of the trial products received from the Sponsor, stored, dispensed to and returned from subjects, and destroyed using appropriate forms. The trial products will be stored at the site at $+2-8^{\circ}\text{C}$ in a place with restricted access. If the Sponsor decides to, all trial product that is returned by subjects will be destructed at the trial site after written approval from the Sponsor, and destruction documented accordingly.

6.5.10 Prior and Concomitant Therapy

Any concomitant medication should be avoided during the entire duration of the trial, except contraceptives. All rescue medications taken during the trial period as well as dietary and herbal supplements will be registered on the appropriate page in the CRF. Use of concomitant medication and supplements during the last year and use of rescue medication from screening visit until end of trial should be documented.

The last 2 months prior to screening, or incidental use in the last 2 weeks prior to screening, and until final examination (Visit 5); all medications (including over-the-counter products and large doses of vitamins and/or mineral) that might have an effect on gut microbiota, gut regularity or gut symptoms, in particular NSAID (e.g. ibuprofen, ASA), laxative and intake of probiotics products are prohibited.

Use of systemic immunosuppressant drugs is not allowed for 4 weeks prior to the screening visit.

Antibiotics and steroids (except contraceptives) are prohibited from 2 months prior to the screening visit until the end of the trial. Subjects taking antibiotics during the trial will be discontinued from the trial.

